In this study, the placebo will consist of inactive tablets identical to the active treatment tablets. Treatment assignments (active drug versus placebo) will be randomized for each patient to the two treatment periods within each block. (see Section F.1.6 for details about the randomization process; the unblinded randomization schema is available to unblinded study team members in Appendix I.

This study is part of Early-Phase Pain Investigation Clinical Network (EPPIC-Net), under The Helping to End Addiction Long-termSM Initiative, or NIH HEAL InitiativeSM.

D. 2. Study Endpoints

D.2.1. Primary Safety Endpoint

The primary safety endpoint is the incidence of treatment emergent adverse events (TEAEs), reported between the administration of study drug on Day 1 and the completion of the study at Week 24 or Early Termination.

D.2.2. Primary Efficacy Endpoint

The primary efficacy endpoint is pain in the index knee, measured weekly using the WOMAC-A (Pain subscale), (Bellamy et al, 1988). We will use the numerical rating scale version of the WOMAC-A, with the subject assessing each of 5 questions using an 11-point (0 to 10) scale; the total score is the sum of the individual item scores (range 0-50). A higher WOMAC-A score represents worse symptom severity.

All WOMAC subscales show strong evidence of validity and reliability (Salafi et al, 2003), and are the most frequently used primary endpoints for OA trials because of their strong assay sensitivity (Jung et al, 2018). Assessments during the last 2 weeks of each treatment period will be used to test the primary hypotheses in order to avoid possible carryover effects of unknown duration. All weekly measurements of WOMAC-A will be used to study the course of OA pain symptoms during treatment, including onset of action and carryover effects.

D.2.3. Secondary Endpoints

The following measures are considered secondary outcomes related to pain due to OA of the knee. They will be assessed at Baseline and at study visits through Week 24. See Section F.1.1 Schedule of Events for full description of procedure timepoints. The Daily Knee Pain Intensity on a 0-10 NRS which will be recorded daily the week prior to each study visit. For a full description of secondary endpoint scales and assessments, see Section F.2.4 and F.2.5.

- Daily Knee Pain Intensity on a 0-10 Numeric Rating Scale (NRS).
- WOMAC-C (Function subscale)
- Hospital Anxiety and Depression Scale (HADS)

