The primary safety endpoint for the study is the following: Percent of adverse events and serious adverse events in the final 2 weeks of each treatment period. Vital signs (heart rate, blood pressure, etc.) will be obtained regularly throughout the study at the time of study visits. Height and weight will be collected during the screening period and at the subject's final study visit. Blood chemistry and hematology panels will also be obtained regularly at study visits. All ECGs will be documented by recording date, time, heart rate, QRS duration, PR interval, RR interval, QT, and QTcF on the eCRF. Paper strips will be maintained in the patient file. If indicated, additional ECG assessments can be made at the discretion of the investigator.

Because CNTX-6970 is metabolized by CYP2C9 and CYP3A4 (to a lesser extent), use of inhibitors and inducers of those two genes are excluded for the duration of participation in the trial. CYP2C9 genotyping will be used to exclude poor metabolizers. As a P-glycoprotein (P-gp) substrate, introduction of any new P-gp inhibitor is also exclusionary for the duration of study participation – P-gp use must have been chronic for at least 3 months and stable for at least 1 month prior to Baseline. Additionally, until more is known about the hepatic metabolism and renal excretion of CNTX-6970, individuals with moderate to severe impairment in hepatic or renal functioning will be excluded from participation.

ECGs will be done at each in-clinic visit to assess heart health. Urine dipstick/urinalysis and liver functioning tests (AST, ALT, GGT, total bilirubin, direct bilirubin, ALK phosphatase) will be collected at each in-clinic visit to monitor the subject's health throughout the study.

F.3. Discontinuation

F.3.1. Discontinuation of Subjects

In accordance with the Declaration of Helsinki and other applicable regulations, subjects have the right to withdraw from the study at any time, and for any reason, without prejudice to their future medical care. Subjects may be discontinued or withdrawn from the study for any of the following reasons:

- Serious adverse event.
- The investigator determines that continuation in the study would be detrimental to a subject's well-being, including criteria under F.3.1.1
- Subject fails to comply with protocol requirements.
- Subject misses more than 6 consecutive doses of study medication.
- Subject is lost to follow-up.
- Subject becomes pregnant.

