F.3.1.1. Automatic Stopping Criteria for Subjects

If a subject meets any of the following criteria at any time during the study, they must be discontinued from the study drug and withdrawn from participation, in accordance with the procedures outlined in Section F.3.2.

- a. 1) ALT and/or AST $>3x$ ULN with total bilirubin $>2x$ ULN (unless elevated bilirubin is related to confirmed Gilbert's Syndrome). Subjects with total serum bilirubin $>2x$ above ULN will be followed until resolution. 2) Confirmed AST and/or ALT $>5x$ ULN for more than 2 weeks.
- b. Serum creatinine $>1.5 \times$ ULN or Grade 2 (moderate) value based on Toxicity Grading Scale for Healthy Adult and Adolescent Volunteers Enrolled in Preventive Vaccine Clinical Trials.

- c. ECGs (minimum criteria): absolute QTcF \geq 500 ms; absolute QTcF $<$ 320 ms (clinically significant QTc shortening); prolongation in repeated, averaged ECG measures of PR or QRS of $>$ 40 ms from the Baseline Visit.
- d. Monocyte count $<$ 1% of white blood cells (e.g., for WBC = 4,500/ μ L, stop if monocyte count $<$ 0.01 * 4,500 or 45/ μ L), hemoglobin $<$ 11 g/dL (Grade 2 in females) or $<$ 12.4 g/dL (Grade 2 in males), platelets $<$ 100,000/ μ L on 2 consecutive blood draws. A confirmatory blood draw will be completed at an in-clinic unscheduled visit. Discontinuation will be confirmed by the consecutive blood draw at the next in-clinic visit.

F.3.2. Discontinuation of Subjects who Stopped taking Study Medication

Should a patient discontinue study medication and decide to withdraw consent, an EOS visit should be scheduled at the earliest convenience to complete the EOS study procedures, unless the subject agrees to schedule it for the next study visit.

Should a patient discontinue study medication, but not withdraw consent, best efforts should be made by the site to collect all study data at the regular study assessment times through the closest of the following study visits: Week 6, Week 12, Week 18 or Week 24/ET. At this clinic visit, all assessments outlined for the EOS visit should be conducted.

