- Concurrent illnesses

F.4.7.3. Duration

The duration of the AE should be recorded using the following criteria:

- Start: Date of the first episode of the AE or date of significant sustained worsening in severity
- Stop: Date when AE either ceased permanently or changed in severity
 - If AE has not resolved/recovered, document as ongoing

In the event that a subject is withdrawn from the study because of an AE, the subject should be followed and treated by the investigator until the AE has resolved, stabilized, or a new chronic baseline has been established.

F.4.7.4. Frequency

The frequency of the AE should be indicated according to the following definitions:

- Single: Experienced once, without recurrence
- Recurrent: More than one discrete episode with the same severity

F.4.7.5. Action Taken with Regard to Study Medication

- Dose not changed
- Drug withdrawn
- Drug interrupted
- Not applicable

F.4.7.6. Outcome

- Recovered/resolved
- Recovered/resolved with sequelae
- Not recovered/not resolved
- Fatal: Death related to adverse event
- Unknown

F.4.7.7. Seriousness

See Section F.4.2. for additional information about determining the seriousness of an AE.

- Not serious
- Serious

F.4.7.8. Expectedness – as determined by the Investigator

An AE is deemed unexpected (in terms of nature, severity, or frequency), given the information provided in research-related documents, such as the Investigator's Brochure (IB), and the characteristics of the subject population being studied.

An adverse event or suspected adverse reaction is considered "unexpected" if the event/reaction is:

- Not listed in the IB;
- Listed in the IB, but not at the specificity or severity that has been observed; or
- Not consistent with the risk information described in the general investigational plan or elsewhere in the current application (per 21CFR312.32).

F.4.8. Reporting Procedures

F.4.8.1. Adverse Event Reporting

The investigator or designee must record all observed AEs and all reported AEs. At each visit, the investigator or designee should ask the subject a nonspecific question (e.g., "Have you noticed

anything different since your last visit?”) to assess whether any AEs have been experienced since the last report or visit.

All AEs, serious and not serious, will be recorded on the AE eCRF page using appropriate medical terminology. Severity and relationship to study drug will be assessed by the investigator as described above.

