### 4.4 Endpoints and Biomarkers

#### 4.4.1 Primary Safety Endpoint

The primary safety endpoint is the incidence of treatment emergent adverse events (TEAEs), reported between the administration of study drug on Day 1 and the completion of the study at Week 24 or earlier if a patient discontinues treatment.

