## 8 Safety Analyses

A primary objective of this trial is to evaluate the safety of CNTX-6970 300 mg BID for the treatment of pain related to OA of the knee compared to placebo. The primary safety endpoint is the incidence of treatment emergent adverse events (TEAEs), reported between the administration of study drug on Day 1 and the completion of the study at Week 24.

**Aim 1:** Assess the safety CNTX-6970 (300 mg BID).

There will be no hypothesis testing under Aim 1. All AEs and SAEs observed during different treatment periods will be summarized based on severity and relation to the active treatment (CNTX-6970 300mg BID). The reports will include tabulation of the AEs and SAEs by period, block, and sequence; point estimates and 95% CIs will be reported. Similarly, we will summarize relevant laboratory measures which include chemistry and Complete Blood Count (CBC) with appropriate estimates.

The primary safety endpoint is the incidence of treatment emergent adverse events (TEAEs), reported between the administration of study drug on Day 1 and the completion of the study at Week 24 or Early Termination. Specifically, the primary safety endpoint for the study is the following: Percent of adverse events and serious adverse events in the final 2 weeks of each treatment period. Vital signs (heart rate, blood pressure, etc.) will be obtained regularly throughout the study at the time of study visits. Height and weight will be collected during the screening period and at the subject's final study visit. Blood chemistry and hematology panels will also be obtained regularly at study visits. All ECGs will be documented by recording date, time, heart rate, QRS duration, PR interval, RR interval, QT, and QTcF on the eCRF. Paper strips will be maintained in the patient file. If indicated, additional ECG assessments can be made at the discretion of the investigator.

The severity of each AE will be graded on a 4-point scale and reported in detail as indicated on the eCRF. Vital signs, systemic effects, and laboratory abnormalities will be graded using the Toxicity Grading Scale

for Healthy Adult and Adolescent Volunteers Enrolled in Preventive Vaccine Clinical Trials, available at <https://www.fda.gov/media/73679/download> (See MOP Appendix M).

- Grade 1 (Mild: No interference with activity)
- Grade 2 (Moderate: Some interference with activity, not requiring medical attention)
- Grade 3 (Severe: Prevents daily activity and requires medical intervention)

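### Two incompatible definitions of the primary safety endpoint: whole-study TEAEs, or a percent of AEs in the final 2 weeks of each period that has no denominator or counting rule

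*SAP*

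**What the plan says.** Both documents attach the label of primary safety endpoint to two different quantities.

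- **Whole-study version.** Protocol D.2.1 defines it as the "incidence of treatment emergent adverse events (TEAEs), reported between the administration of study drug on Day 1 and the completion of the study", ending at Week 24 or early termination. SAP 4.4.1 is nearly the same but closes the interval at "completion of the study at Week 24 or earlier if a patient discontinues treatment". SAP 8 states this version twice.
- **Final-2-weeks version.** Protocol F.2.7 says, with the window applied to every period: "The primary safety endpoint for the study is the following: Percent of adverse events and serious adverse events in the final 2 weeks". SAP 8 repeats this directly after its second statement of the whole-study version and offers it as the specific form: "Specifically, the primary safety endpoint for the study is the following: Percent of adverse events and serious adverse events in the final 2 weeks".

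The Aim 1 analysis text uses no window: "All AEs and SAEs observed during different treatment periods will be summarized based on severity and relation to the active treatment". It plans point estimates with 95% confidence intervals and no hypothesis test. SAP 4.1.1 and Protocol C.1 plan AE and SAE frequencies for the active and placebo groups, also without a window.

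The AE record holds start and stop dates. Protocol F.4.7.3 defines the start as follows: "Start: Date of the first episode of the AE or date of significant sustained worsening in severity".

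**The concern.** Safety is part of the primary objective (Aim 1), and the plan leaves open which number is its primary result. An analyst who follows the last and most specific-sounding sentence of SAP 8 would take the headline figure from one third of follow-up. The same choice would pass to the discontinued 100 mg and celecoxib arms (n=22), because Protocol C.4 has their safety analysed in the same way.

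The documents justify a last-2-weeks window only for WOMAC-A, where it is meant to let carryover fade (SAP 9.1, Protocol K.2). They give no reason for applying it to adverse events. For AEs it would remove the weeks just after each treatment switch.

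Subjects who leave because of an AE are also at risk of dropping out of the count. Those who meet an automatic stopping criterion are covered by Protocol F.3.1.1: "they must be discontinued from the study drug and withdrawn from participation". For those who stop drug without withdrawing consent, F.3.2 asks for best efforts to collect data "through the closest of the following study visits: Week 6, Week 12, Week 18 or Week 24/ET". A subject who leaves in weeks 1–4 of a period may therefore have no final-2-weeks window in that period.

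**Working it through.** The documents state no rate, sample size or power for safety, so there is no safety figure to reproduce. The check compares the two definitions and then works out what the narrow one leaves out.

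**Comparison of the two definitions**

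| Feature | Whole-study version | Final-2-weeks version |
|---|---|---|
| Interval | First dose to Week 24 or early termination | Weeks 5–6 of each 6-week period |
| Events | Treatment-emergent AEs | AEs and SAEs, no treatment-emergent restriction |
| Measure | Incidence | Percent, with no stated denominator |

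**Coverage.** There are four periods of 6 weeks (SAP 5.1).

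- Follow-up inside a window: 4 × 2 = 8 of 24 weeks = 33.3%.
- Drug exposure inside a window, per subject: 2 × 2 = 4 of 12 weeks.
- SAP 5.3 gives the sequences Drug:Placebo:Placebo:Drug and Placebo:Drug:Drug:Placebo. New starts of drug fall at periods 1 and 4 in the first sequence and at period 2 in the second. In each case the first four weeks lie outside a window.

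**Share of AEs missed.** Assume constant onset over a 6-week period.

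- Counted by onset: 4/6 = 67%.
- Counted by presence, with a fixed duration of d weeks: max(0, 4 − d)/6. This gives 3/6 = 50% for d = 1, 2/6 = 33% for d = 2, and 0% for d = 4 or more. The durations are assumed.
- If onset falls off after each period starts, with an assumed half-life of 1, 2 or 4 weeks, only 5%, 14% or 23% of onsets fall in weeks 5–6.

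**Effect of the missing denominator.** As an illustration, assume 0.5 AEs per subject per 6 weeks at a constant rate, full follow-up, and counting by onset. The rate is not in the documents. The same data then give these readings of percent:

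- Subjects with an AE in one window: 1 − exp(−0.5/3) = 15%.
- Subjects with an AE in either drug window: 1 − exp(−2 × 0.5/3) = 28%.
- Window AEs as a share of all AEs: 2/6 = 33%.
- Subjects with an AE in any of the four windows: 1 − exp(−4 × 0.5/3) = 49%.

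The whole-study proportion of subjects with an AE would be 1 − exp(−4 × 0.5) = 86%.

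**Periods with no window.** The inputs are n = 55 and 15% early termination per period (SAP 6). As a check on these inputs, completers are 55 × 0.85⁴ = 28.7, and SAP 6 states about 29.

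- Subjects starting each period: 55 + 46.75 + 39.74 + 33.78 = 175.26 subject-periods.
- Subjects leaving: 8.25 + 7.01 + 5.96 + 5.07 = 26.29.
- With leaving times uniform over 6 weeks, departures before the window are 26.29 × 4/6 = 17.5, or 10% of started periods. The range is 0 (all leave in weeks 5–6) to 26.29, or 15% (all leave in weeks 1–4).
- Subjects with no window at all, having left in weeks 1–4 of period 1: 8.25 × 4/6 = 5.5, or 10% of 55. The range is 0 to 8.25, or 15%.

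**The case against.** The contradiction itself is not in dispute. The case on the other side concerns how much it matters and how far the remedy should go.

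- **Most of the reporting is already planned.** AE and SAE frequencies for active and placebo, with confidence intervals and no window, are in the plan. Safety is not tested, and the study stopping rules in Protocol F.3.3.1 apply at any time. The dedicated endpoint sections and the Aim 1 text favour the whole-study version. All of this stands and limits the consequence to which figure carries the primary label. It does not settle the label, because no text gives precedence and SAP 8 presents the narrow version as the specific one.
- **The loss of AE leavers may be overstated.** F.3.1.1 sends subjects who meet a stopping criterion through the F.3.2 procedures, and the F.3.2 visits coincide with period ends. F.4.7.3 has subjects withdrawn for an AE followed until it resolves or stabilises. This partly stands: follow-up could recover some windows, and the 15% covers every reason for leaving. But following one event to resolution does not create a final-2-weeks observation window, and the plan does not say whether such subjects enter the denominator.
- **The whole-study version is also loose.** Incidence is not tied to subjects or events, TEAE is spelled out but not defined, and no rule assigns an AE that spans two periods. This stands, so choosing that version is not enough without a unit and an attribution rule.
- **Attribution by onset can misplace carryover.** Periods follow one another without a drug-free gap, so a drug-related AE could start early in a placebo period. This is a fair limitation. A flag on those AEs would show its extent.

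**Conclusion.** The concern holds. This is a direct conflict in the current text of both documents, and the narrow definition cannot be computed as written.

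The coverage figures (8 of 24 weeks, 4 of 12 drug-weeks) follow from the design alone. The shares of AEs missed depend on the assumed onset pattern and durations. The figure of about 10% of started periods without a window (range 0–15%) rests on the plan's all-cause termination rate, an assumed timing of departure, and no recovery through follow-up.

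No error rate or power is affected and no AE data are lost. What is at stake is the headline safety estimate for a primary aim, and the room to choose between two primary definitions after seeing the results. It should be corrected.

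**What to change.** 1. Delete the final-2-weeks sentence from Protocol F.2.7 and SAP 8. If it is kept, label it supplementary and state its denominator and whether an AE counts by onset or by presence.
2. Use the Protocol D.2.1 definition throughout. Report the proportion of subjects with at least one TEAE, and separately at least one SAE, with onset during each treatment. The denominator is the subjects who received that treatment. Give a 95% confidence interval for each. A subject who leaves during period 1 then counts only under the treatment received.
3. Take onset from the F.4.7.3 start date, which already covers sustained worsening. This also settles AEs that continue into the next period.
4. Align the end of the interval in SAP 4.4.1 with Week 24 or early termination. Its present wording could drop AEs in subjects who stop treatment but remain in follow-up.
5. Optionally, flag AEs that start early in a placebo period directly after drug (period 2 in one sequence, period 4 in the other).

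The cost is a short amendment to the protocol, which goes to the central IRB, and to the SAP. No new data are needed: AEs are recorded from consent with start and stop dates (Protocol F.4.1, F.4.7.3). The change should be settled before the sequence codes are released.

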## 9 Efficacy Analyses

This section describes the statistical analyses for the objectives defined by the aims and hypotheses described in Section 4.

### 9.1 Primary Efficacy Analysis

For the efficacy Aim 2, data from the WOMAC Part A (WOMAC-A) assessed only in the last two weeks of each 6-weeks treatment period will be used for this primary analysis in order to avoid any carryover effects, which are expected to vanish after 4 weeks. Hypothesis 1 in Section 4 will be tested using the following random-effects multi-period crossover model that employs block and period effects to compare the active treatment to placebo (Zucker *et al.*, 1997; Chen and Chen, 2014). Specifically, the model is:

$$y_{i(s)jkm} = \beta_0 + \gamma_j + \delta_k + \beta_1 X_{i(s)jk} + \beta_2' \mathbf{w}_{i(s)} + b_s + b_{i(s)} + \epsilon_{i(s)m}, \quad (1)$$

where  $i(s)$  is the index for patient  $i$  at site  $s$ ;  $\beta_0$  is the intercept;  $j$  is the index for block,  $j = 1, 2$  and  $\gamma_j$  is the block effect;  $k$  is the index for period,  $k = 1, 2$ , and  $\delta_k$  is the period effect;  $m$  is the measurement time;  $y_{i(s)jkm}$  is the primary outcome for subject  $i(s)$ , block  $j$ , period  $k$ , time  $m$ ;  $\beta_1$  represents the treatment effect, and  $X_{i(s)jk}$  is an indicator for active treatment ( $X_{i(s)jk} = 1$ ) or placebo ( $X_{i(s)jk} = 0$ ) for patient  $i(s)$ , in block  $j$ , during period  $k$ ;  $\mathbf{w}_{i(s)}$  is a vector of baseline characteristics (e.g., age, sex, K-L grade indicator) for patient  $i(s)$  and  $\beta_2$  is a vector of coefficients for those baseline characteristics;  $b_s \sim N(0, \sigma_{site}^2)$  is a random site effect and  $b_{i(s)} \sim N(0, \sigma_b^2)$  is a subject-level random effect (nested within site);  $\epsilon_{i(s),m}$  is a random error with an  $AR(1)$  structure:  $\epsilon_{i(s),m} = \phi \epsilon_{i(s),m-1} + u_{i(s)m}$ , with  $u_{i(s)m} \sim N(0, \sigma_u^2)$ . The subject-level random effects will model the repeated measures within subjects. The block and period effect terms will accommodate changes in mean pain scores across blocks and periods of the design.

The primary hypothesis of interest for this model is  $H_0 : \beta_1 = 0$  versus  $H_a : \beta_1 \neq 0$ . Maximum likelihood estimation will be used to estimate the model parameters using the statistical software R and likelihood ratio tests will be performed to test and obtain  $p$ -values for the hypotheses of treatment effects (active versus placebo) for the active treatment. Under the null hypothesis, the likelihood ratio test will have an approximate chi-square distribution with 1 degree of freedom. The hypothesis testing proposed here is based on the WOMAC-A assessed only in the last 2 weeks of each 6-week treatment period. This provides a more than adequate 4-week washout interval for CNTX-6970. The adequacy of this 4-week period is based on extensive pharmacokinetics (PK) and pharmacodynamics (PD) of the study agent CNTX-6970 provided in the Centrexion dossier.

Additionally, for the analysis under Aim 3 described below, we explicitly model the potential carryover effects using model (2),

The proposed model (2) utilizes a standard approach to adjust for carryover effects in a multi-period crossover design when estimating the treatment effect, and allows for testing for the existence of carryover effect (Chen and Chen, 2014).

